#### Analyses of Key Secondary Efficacy Variables

The test for the following secondary estimates based on continuous variables will use the MMRM model in the FAS population, as described for the primary analysis:

- Difference at Week 8 in QIDS-SR16 mean change from baseline.
- Difference at Week 8 in mean % improvement from baseline in SIGH-D-17 scores.
- Difference at Week 8 in mean % improvement from baseline in QIDS-SR16 scores.

- Difference at Week 8 in mean change from baseline of CGI-S.

The Mantel-Haenszel method, stratified by investigative site, in the FAS population, will test AGT vs TAU estimates based on categorical variables:

- Difference in % treatment responders at Week 8, done separately for SIGH-D-17, QIDS-SR16 and CGI-I. Treatment response is defined as  $\geq 50\%$  reduction of SIGH-D-17 from baseline to Week 8 for blinded rater assessment,  $\geq 50\%$  reduction of QIDS-SR16 from baseline to Week 8 for subject-rated assessment, score of  $\leq 3$  on the CGI-I from baseline to Week 8 for the unblinded clinician assessment. If Treatment Response is missing at Week 8, the subject will be considered a Week 8 treatment non-responder. The two-sided p-value, estimated odds ratio and 95% CI for the odds ratio will be computed.
- Difference in % treatment remitters, done separately for SIGH-D-17 and QIDS-SR16, at Week 8. Remission is defined as score of ≤ 7 on the SIGH-D-17 from baseline to Week 8 for blinded rater assessment, score of ≤ 5 on the QIDS-SR16 from baseline to Week 8 for subject-rated assessment. If Treatment Remission is missing at Week 8, the subject will considered a Week 8 treatment non-responder. The two-sided p-value, estimated odds ratio and 95% CI for the odds ratio will be computed
- Difference at Week 8 in CGI-I profile.

#### 

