## 2 STATISTICAL AND ANALYTICAL PROCEDURES

**Note:** Unless stated otherwise, this section applies to both the Main Study and the Exploratory Elderly MDD Study. Procedures, in general, may be adjusted in the Exploratory Elderly MDD Study to reflect sparse sample sizes, eg, substitution of a short listing in place of a full table.

Summarizations will be provided in tables and figures. Safety and efficacy variables will be summarized by visit using descriptive statistics. For continuous variables, this will include the number of non-missing values, mean, standard deviation (SD) or standard error of the mean, median, minimum, and maximum. Categorical variables will be summarized using counts and percentages.

Unless otherwise stated, the significance level for statistical tests will be two-sided, alpha=0.05, with no adjustment for multiple comparisons

Pooled Investigative Sites: For all statistical analyses, sites with few subjects (< 7 subjects) will be pooled into a single larger site. "Investigative site" in all statistical analyses will refer to "sites" as pooled.

SIGH-D-17 interviews will be reviewed by central expert monitors, and site SIGH-D-17 scores may be revised based on the central monitor evaluation. All SIGH-D-17 changes due to central review will be described by listings. SIGH-D-17 statistical analyses, summaries, and listings will otherwise rely solely on the revised SIGH-D-17 scores. Note, SIGH-D-17 inclusion criteria are based on the original site rater screening and baseline SIGH-D-17, irrespective of any later revision after central review.

**Note:** No central rater evaluation will be done for the Exploratory Elderly MDD Study, as the sites enrolling subjects will continue from the Main Study and already have trained, experienced site raters.

Data will be reported and analyzed using SAS software, version 9.3, except as noted otherwise.

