#### 2.1 Efficacy Analysis Estimands

This trial is a comparison of outcomes between two treatment strategies, evaluated at 8 weeks. For practical interpretation, this implies the statistical analyses should estimate and test the difference in Week 8 outcomes for all subjects, irrespective of attrition or compliance. [This may also be described as following the Intent to Treat (ITT) principle, but there is confusion about the use of this term when there is missing data, and ITT terminology will not be used further here.]. Specifying the "estimands") (what is being estimated), aligned with the study purpose, is the basis for the formal statistical methods which follow.

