### Secondary Efficacy: AGT vs TAU

- Difference at Week 8 in QIDS-SR16 mean change from baseline, for all randomized subjects.
- Difference in % treatment responders at Week 8, for all randomized subjects. Treatment response will be defined in 3 different ways:

 $\geq$  50% reduction of SIGH-D-17 from baseline for blinded rater assessment

≥ 50% reduction of QIDS-SR16 from baseline for subject-rated assessment

Score of  $\leq$  3 on the CGI-I from baseline for the unblinded clinician assessment

• Difference in % treatment remitters at Week 8, for all randomized subjects. Remission is defined for the SIGH-D-17 and the QIDS-SR16:

Score of  $\leq$  7 on the SIGH-D-17 from baseline for blinded rater assessment

Score of  $\leq$  5 on the QIDS-SR16 from baseline for subject-rated assessment.

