#### Analyses of Key Secondary Efficacy Variables

The major emphasis will be on descriptive statistics and confidence intervals. Nominal p-values will also be computed.

The following secondary continuous variables will use the same LOCF ANCOVA model described for the primary analysis. Two-sided p-values, LS means and CIs for TAU - AGT difference at for Week 8 will be computed.

- Difference at Week 8 in QIDS-SR16 mean change from baseline.
- Difference at Week 8 in mean % improvement from baseline in SIGH-D-17 scores.
- Difference at Week 8 in mean % improvement from baseline in QIDS-SR16 scores.
- Difference at Week 8 in mean change from baseline of CGI-S.

Similarly, the Mantel-Haenszel method, stratified by investigative site, in the FAS population, will test AGT vs TAU based on categorical variables. The two-sided p-value, estimated odds ratio and 95% CI for the odds ratio will be computed:

- Difference in % treatment responders at Week 8, done separately for SIGH-D-17, QIDS-SR16 and CGI-I. Treatment response is defined as  $\geq$  50% reduction of SIGH-D-17 from baseline to Week 8 for blinded rater assessment,  $\geq$  50% reduction of QIDS-SR16 from baseline to Week 8 for subject-rated assessment, score of  $\leq$  3 on the CGI-I from baseline to Week 8 for the unblinded clinician assessment. If Treatment Response is missing at Week 8, the subject will be considered a Week 8 treatment non-responder.
- Difference in % treatment remitters, done separately for SIGH-D-17 and QIDS-SR16, at Week 8. Remission is defined as score of ≤ 7 on the SIGH-D-17 from baseline to Week 8 for blinded rater assessment, score of ≤ 5 on the QIDS-SR16 from baseline to Week 8 for subject-rated assessment. If Treatment Remission is missing at Week 8, the subject will considered a Week 8 treatment non-responder.
- Difference at Week 8 in CGI-I profile.

End of Efficacy Analyses for the Exploratory Elderly MDD Study

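### Response and remission estimands are differences in percentages, but the only comparative estimate planned is an odds ratio; a site-stratified difference with a 95% CI should be added

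*SAP*

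**What the plan says.** SAP 2.1 makes the estimands the starting point for the methods and states that "the statistical analyses should estimate and test the difference in Week 8 outcomes for all subjects, irrespective of attrition or compliance". Under Secondary Efficacy it lists "Difference in % treatment responders at Week 8, for all randomized subjects" and "Difference in % treatment remitters at Week 8, for all randomized subjects". Protocol 8.2.1 (Secondary Efficacy) defines the same two quantities.

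SAP 3.4 (Analyses of Key Secondary Efficacy Variables) sets the method: "The Mantel-Haenszel method, stratified by investigative site, in the FAS population, will test AGT vs TAU". The differences in responder and remitter percentages are named as the items analysed, and the output for each is "The two-sided p-value, estimated odds ratio and 95% CI for the odds ratio will be computed". On missing data it says: "If Treatment Response is missing at Week 8, the subject will be considered a Week 8 treatment non-responder"; remission is treated in the same way. Protocol 9.4.4 gives the same method and output for the Main Study. The SAP's Elderly Study section also asks for "The two-sided p-value, estimated odds ratio and 95% CI" for the odds ratio.

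The only planned output on the percentage scale is the general rule in SAP 2: "Categorical variables will be summarized using counts and percentages". On the population, SAP 2.4 acknowledges that the estimands cover all randomized patients, explains why the FAS is used, and adds sensitivity analyses on the All Randomized Set if the FAS falls below 95% of it.

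**The concern.** The plan names one quantity as its target and specifies an estimate and interval for another. The continuous endpoints do not have this problem: the primary analysis in SAP 3.4 promises a 95% CI for the difference in Week 8 means, which is the scale of its estimand.

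An odds ratio and its interval do not determine the difference in percentages. The conversion depends on the TAU rate, and the documents assume no rate for any response or remission endpoint. The site-stratified odds ratio is also a within-site measure, and odds ratios are non-collapsible, so it need not equal the odds ratio formed from the overall arm percentages.

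At stake is whether the report carries a pre-specified interval for the absolute difference in response and remission. Without one, any interval for that difference would have to be built afterwards by a method chosen after the fact.

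**Working it through.** **The plan's own figure.** There is none for these endpoints. The stated sample size concerns the primary mean difference: 115 per group, and 115/0.77 = 149.4, rounded up to 150 per group at 23% dropout. It reproduces but does not bear on this point. Below, 150 per arm serves only as an illustrative denominator.

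**Target against output.** Target (SAP 2.1, Protocol 8.2.1): p1 − p0 at Week 8, where p1 is the AGT rate and p0 the TAU rate. Output (SAP 3.4, Protocol 9.4.4): p-value, odds ratio, CI for the odds ratio. Neither document specifies a CI for p1 − p0.

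**From odds ratio to difference.** Inputs are assumed: p0 from 10% to 50%, an odds ratio of 1.5 or 2.0, 150 per arm, and an unstratified Wald interval.

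- p1 = OR × p0/(1 − p0) ÷ [1 + OR × p0/(1 − p0)]
- SE = √[p0(1 − p0)/150 + p1(1 − p1)/150]
- 95% CI = (p1 − p0) ± 1.96 × SE

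Example, p0 = 0.30 and OR = 1.5: odds 0.4286 × 1.5 = 0.6429, so p1 = 0.6429/1.6429 = 0.391. The difference is 9.1 points, SE = 0.0547, and the CI is 9.1 ± 10.7, or −1.6 to 19.8.

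| Assumed TAU rate | Difference at OR 1.5, points (95% CI) | Difference at OR 2.0, points (95% CI) |
|---|---|---|
| 10% | 4.3 (−3.1 to 11.7) | 8.2 (0.4 to 16.0) |
| 20% | 7.3 (−2.3 to 16.9) | 13.3 (3.4 to 23.2) |
| 30% | 9.1 (−1.6 to 19.8) | 16.2 (5.3 to 27.0) |
| 40% | 10.0 (−1.2 to 21.2) | 17.1 (6.0 to 28.3) |
| 50% | 10.0 (−1.2 to 21.2) | 16.7 (5.7 to 27.7) |

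Protocol 1.1 quotes remission rates of 30.6%, 13.7% and 13.0% at the steps after a first failed treatment, and this trial requires at least one failure. If TAU remission took those values, an odds ratio of 1.5 would give p1 = 39.8%, 19.2% and 18.3%, which are differences of 9.2, 5.5 and 5.3 points.

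The reverse also holds. A 10-point difference is an odds ratio of (0.30 × 0.80)/(0.20 × 0.70) = 1.71 at 30% vs 20%, and (0.65 × 0.45)/(0.55 × 0.35) = 1.52 at 65% vs 55% (rates assumed).

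**What the same data can give.** The Mantel-Haenszel risk difference is Σ w_k(p1k − p0k)/Σ w_k over pooled sites k, with w_k = n1k·n0k/(n1k + n0k). With 1:1 allocation within site, w_k is close to n_k/4. The estimate is then close to a site-size-weighted average of the site differences, which is the stated target.

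**FAS against all randomized.** Assume FAS rates of 40% vs 30% and count everyone outside the FAS as a non-responder.

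- 95% of each arm in the FAS: 0.40 × 0.95 − 0.30 × 0.95 = 9.5 points.
- 92% of AGT and 98% of TAU: 0.368 − 0.294 = 7.4 points.
- 98% of AGT and 92% of TAU: 0.392 − 0.276 = 11.6 points.

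In the two unbalanced cases the FAS holds 138 + 147 = 285 of 300, exactly 95%, so the sensitivity analysis would not be triggered.

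**The case against.** The strongest reply is that nothing essential is lost. SAP 3.4 names the difference in percentages as the item analysed, the percentages are tabulated, Mantel-Haenszel tests them, and the odds ratio is simply the accompanying effect measure. Anyone with the counts per arm can form a crude difference and an unstratified interval. Much of this stands. What it does not provide is a pre-specified, site-stratified interval, although randomization and the planned test are both stratified by site.

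Several stronger readings are tempting, and the documents do not support them.

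- A reader might infer that the plan reports nothing but an odds ratio. It also specifies the p-value and the percentages.
- A reader might infer that the test is compromised. No treatment difference within sites is the same null hypothesis on either scale, so non-collapsibility does not affect the planned p-value.
- A reader might infer that the odds ratio exaggerates the benefit. It is a relative measure and the estimand an absolute one; the mismatch is one of scale, and no rates are given from which to show exaggeration.
- A reader might infer that the plan overlooks randomized subjects outside the FAS. SAP 2.4 addresses them, and with equal exclusions the shift at the 95% threshold is small (10.0 to 9.5 points). A larger shift needs an assumed imbalance. The 37% vs 18% dropout in the reference study is overall dropout, not exclusion from an FAS.

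Making the all-randomized set the main analysis would also have a price. It could bring back the subject treated before randomization, whom SAP 2.4 excludes from the FAS, and it would put these endpoints on a different set from the continuous secondaries. That argues for a supporting analysis.

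**Conclusion.** The mismatch is real and appears in the protocol, the SAP's Main Study section and its Elderly Study section. The plan states a difference in percentages as the estimand and specifies no stratified estimate of it and no interval for it. For assumed TAU rates of 10% to 50%, an odds ratio of 1.5 leaves the difference anywhere from about 4 to 10 points. That range illustrates the gap and does not forecast results, because the documents give no planning rates for these endpoints.

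The consequence is limited to estimation and reporting of secondary endpoints. In the Elderly Study the interval carries more of the interpretation, because the SAP there puts its main emphasis on descriptive statistics and confidence intervals. The change is worth making because it is nearly free and makes the plan deliver what it says it will estimate.

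**What to change.** In SAP 3.4, for each response endpoint (SIGH-D-17, QIDS-SR16, CGI-I) and each remission endpoint (SIGH-D-17, QIDS-SR16), in both studies:

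1. Add the Mantel-Haenszel risk difference, AGT minus TAU, stratified by pooled site, with a 95% CI, in the FAS. Name it as the estimate of the stated estimand. Keep the planned p-value and odds ratio.
2. Report the same difference on all randomized subjects, with missing counted as non-response or non-remission, as a supporting analysis whether or not the FAS falls below 95%. The plan already applies this rule within the FAS, so no modelling is needed.
3. State how the subject treated before randomization is handled in the supporting analysis.

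Redefining the estimand as an odds ratio would also remove the contradiction, but would leave the difference in percentages without an interval.

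The cost is one or two extra lines per table. SAP 4.0 says it leaves the Main Study analyses unchanged. If the Main Study is already unblinded, the addition should be disclosed in the CSR, as Protocol 8.1 requires for revisions after unblinding. For the Elderly Study it can be pre-specified if those data are still blinded.

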## Efficacy Analyses for Exploratory Elderly MDD Study

#### Primary Analysis

The Exploratory Elderly MDD Study primary analysis will test the Difference at Week 8 in mean SIGH-D-17 change from baseline in a Last Observation Carried Forward ANCOVA, adjusting for baseline SIGH-D-17 and pooled site, in the FAS set. Descriptive statistics and confidence intervals will also be calculated. The Treatment x Pooled Site and Treatment x Baseline SIGH-D-17 interaction tests, as well as diagnostics for outliers, non-normality and other model assumptions will be run, and followed up, as appropriate.

#### Subgroup Analyses

Consistency of AGT vs TAU treatment effect on SIGH-D-17 will be assessed across subgroup factors described below, by evaluating the treatment by subgroup interaction in the LOCF ANCOVA model. If there is evidence of inconsistency of treatment effect (i.e., p-value <0.10 for interaction test), further analyses may be performed. Subgroups will include Gender, Baseline SIGH-D-17 (categorized as in the Main Study, continuous baseline SIGH-D-17 not in the model) and Pooled Site. Confidence intervals for the TAU minus AGT LS Mean Differences for each subgroup factor will be graphically displayed.

#### Analyses of Key Secondary Efficacy Variables

The major emphasis will be on descriptive statistics and confidence intervals. Nominal p-values will also be computed.

The following secondary continuous variables will use the same LOCF ANCOVA model described for the primary analysis. Two-sided p-values, LS means and CIs for TAU - AGT difference at for Week 8 will be computed.

- Difference at Week 8 in QIDS-SR16 mean change from baseline.
- Difference at Week 8 in mean % improvement from baseline in SIGH-D-17 scores.
- Difference at Week 8 in mean % improvement from baseline in QIDS-SR16 scores.
- Difference at Week 8 in mean change from baseline of CGI-S.

Similarly, the Mantel-Haenszel method, stratified by investigative site, in the FAS population, will test AGT vs TAU based on categorical variables. The two-sided p-value, estimated odds ratio and 95% CI for the odds ratio will be computed:

- Difference in % treatment responders at Week 8, done separately for SIGH-D-17, QIDS-SR16 and CGI-I. Treatment response is defined as  $\geq$  50% reduction of SIGH-D-17 from baseline to Week 8 for blinded rater assessment,  $\geq$  50% reduction of QIDS-SR16 from baseline to Week 8 for subject-rated assessment, score of  $\leq$  3 on the CGI-I from baseline to Week 8 for the unblinded clinician assessment. If Treatment Response is missing at Week 8, the subject will be considered a Week 8 treatment non-responder.
- Difference in % treatment remitters, done separately for SIGH-D-17 and QIDS-SR16, at Week 8. Remission is defined as score of ≤ 7 on the SIGH-D-17 from baseline to Week 8 for blinded rater assessment, score of ≤ 5 on the QIDS-SR16 from baseline to Week 8 for subject-rated assessment. If Treatment Remission is missing at Week 8, the subject will considered a Week 8 treatment non-responder.
- Difference at Week 8 in CGI-I profile.

End of Efficacy Analyses for the Exploratory Elderly MDD Study

#### 3.5 Safety Analyses

**Note:** This section applies to both the Main Study and the Exploratory Elderly MDD Study, although safety analyses may be adjusted in the Exploratory Elderly MDD Study to reflect sparse sample sizes, eg, substitution of a short listing in place of a full table.

All safety analyses will be performed on the SAF dataset.

• Adverse events

The analysis will focus on the TEAEs. TEAEs will consist of all AEs with start date after Baseline. Continuing pre-Baseline AEs which worsen in severity or seriousness will be reported in the CRF as new AEs, and thus will be TEAEs. TEAEs will be summarized and tabulated according to body system and frequency for each treatment group. Separate tabulations of AEs depending on seriousness, severity, relationship to MDD treatment, action taken and outcome will be given. SAEs will be correspondingly summarized.

• FIBSER and PRISE

Overall and by visit results from the FIBSER and PRISE scales will be summarized descriptively by treatment.

#### **Other Analyses**

All other endpoints will be descriptively summarized, including the Pre-Result and Post-Result Clinical Decision Survey Findings.

## 3.6 Interim Analysis

No interim analysis is planned for this study.

# 4 SAMPLE SIZE JUSTIFICATION

Sample size is calculated for the primary endpoint, improvement from baseline to eight weeks in the SIGH-D-17 of subjects with Major Depressive Disease.

As there are few studies comparing MDD AGT vs TAU, information to guide sample size is limited.

Nevertheless, three controlled MDD trials of AGT vs TAU provide some quantitative basis for sample size. All are single center, 8-10 weeks in duration, measured SIGH-D-17, and utilized the AssureRx assay battery. For each study an approximate SIGH-D-17 Delta and SD were approximated from tables and figures in the report publication. Delta is the between group difference in mean SIGH-D-17 change and SD is the assumed constant standard deviation of the individual subject's change in HAMD). Cohen's d = Delta/SD was further calculated. Brief summaries of the three studies follow:

- Hall-Flavin DK et al 2012, Using a pharmacogenomic algorithm to guide the treatment of depression. This was the pilot study for next trial in this list: non-randomized, open, single center, comparison of pharmacogenomic guided treatment vs usual treatment for 8 weeks. N=51, 44 analyzed. Dropout rate = 14%. Approximate Delta and SD = 3.5 and 6.0. Approximate delta/SD ratio= 0.58
- 2) Hall-Flavin DK et al 2013.Utility of integrated pharmacogenomic testing to support the treatment of major depressive disorder in a psychiatric outpatient setting. Non-randomized, open, single center, comparison of pharmacogenomic guided treatment vs usual treatment for 8 weeks. N=227, 165 analyzed. The dropout rate = (27%) with 37% AGT vs 18% TAU dropout. The approximate delta and SD are 3.1 and 7.2. Approximate delta/SD ratio= 0.43
- 3) Winner JG et al 2013. A prospective, randomized, double-blind study assessing the clinical impact of integrated pharmacogenomic testing for major depressive disorder. Pilot study, randomized, single center, blinded subject and rater, comparison of pharmacogenomic guided treatment vs usual treatment for 10 weeks. (Although described as double-blind, the Winner study does not meet the minimum conventional double-blind standard blinded investigator and subject) N=51, 49 analyzed. The approximate Week 8 delta/SD ratio=0.47. This ratio was

extrapolated from the % SIGH-D-17 improvement results, and is likely an overestimate of the mean SIGH-D-17 improvement ratio.

The three studies are consistent with one another. The small pilot studies show evidence of efficacy, but are too small for reliable inference. Study 1 greatest observed efficacy (Cohen's d =0.58). The second pilot study (Study 3), is more rigorous, adding randomization and rater/subject blinding, with extrapolated Cohen's d = 0.47, not statistically significant.

The largest study (Study 2) shows a somewhat lower Cohen's d (0.43), a more reliable result due to the much larger sample size and the added sensitivity analyses to assess robustness. Accepting that there remains potential bias due to the non-randomized, open design, this study result was used as the best available basis for sample size calculation.

The sample size is calculated for the two-sided alpha=0.05, 90% power test of two independent means of improvement in SIGH-D-17. In this case the sample size depends only on the postulated Cohen's d, and the % dropouts. Note this should be a conservative estimation of sample size, as the actual analysis will use a more efficient MMRM method. However, this conservatism is balanced by the potential underestimation of needed sample size due to design bias in the reference study.

Using the Trial 2 observed difference in SIGH-D-17 improvement and variability, with resulting Cohen's d=0.43, the resulting sample size is 115 per group, with no dropouts. If we assume the dropout rate somewhat less than the reference (23% vs 27% reference), then with the conventional dropout correction, the needed sample size per group is 150, or 300 total randomized subjects. The table below summarizes the design properties of this size study, under varying assumptions for delta, power and % missing Week 8 SIGH-D-17 assessment. The statistical testing significance level is two-sided alpha < 0.05, and the SD is assumed to be the same (7.2).

Total Sample Size	Subject SD	Delta	Power	% Missing Week 8
300	7.2	3.09	90%	23%
300	7.2	2.67	80%	23%
300	7.2	2.94	90%	15%
300	7.2	2.54	80%	15%
300	7.2	2.85	90%	10%
300	7.2	2.46	80%	10%
300	7.2	2.70	90%	0%
300	7.2	2.34	80%	0%

Detectible\* Delta for Varying Power and Missing Data Assumptions

\*Detectible delta is the smallest postulated "true" difference between means for which 80% (or 90%) of trials would be statistically significant with the given % missing Week 8 data.

All sample size calculations used Stata Version 13 software.

As reiterated above, the reference study is not a definitive foundation for sample size calculation. However, it may be expected the following would hold:

- The base planning SIGH-D-17 delta, at 3.1, is a high bar for an active vs active treatment depression trial. Commonly, the planning delta for placebo controlled depression trials is 3.0 (SIGH-D-17 units) and active vs active studies can expect delta of 1.5 or less and may often designed as non-inferiority studies. It could be argued that a planning delta should be 2.5 or less.
- 2) We expect the SD for this study should be less than the reference study. SIGH-D-17 will be assessed by blinded, trained SIGH-D-17 raters, centrally monitored by an independent group. This reduces bias and improves precision, and should result in the primary endpoint being more accurate, with a smaller SD. A reduction of the SD by 15% seems reasonable (SD=6.12).
- 3) We expect the 8-week dropout rate will be considerably less than the reference, as well as the nominal 23% used in the base sample size calculation. As discussed in Section 8.1, as this trial will institute measures to reduce missing data, consistent with the recommendations by the 2010 NRC Missing Data panel. This, combined with the observed lower dropout rate in active vs active trials, suggests a target of 10% dropouts is realistic.

Assuming the improved rigor of the trial conduct reduces the SD by 15% and the dropout rate to 10%, then with 300 randomized subjects and a 0.05 2-sided test, the "detectable delta" is more realistic: 2.42 with 90% power, and 2.09 with 80% power.

